2.3.4 To observe improvement in psychological resilience and flexibility skills in participants
2.3.5 To reduce feelings of helplessness.
2.3.6 To increase distress tolerance.

Cancer within a Pandemic: A Telemental Health Intervention Designed to Augment Psychological Resilience amidst Dual Health Threats

Wake Forest Baptist Comprehensive Cancer Center
WFBCCC #01520

3 Patient Selection

Recruitment:

Investigators will attempt to recruit prospective participants through:

- Informing oncologists, APPs, and other clinicians who work with potentially eligible patients
- Advertising through hospital channels (clinic flyers, waiting room TVs, intranet postings)
- Contacting YAs who have participated in former clinical or research offerings and shared their contact information (existing databases from Psychosocial Oncology and Public Health Sciences)
- Existing psychosocial oncology caseload

Experienced Investigators within the Psychosocial Oncology group will reach out to identified patients telephonically for introduction and pre-screens. The study will be explained and patients will be asked to answer the questions on the Pre-Screening form. Individuals who are interested in participating but do not meet eligibility criteria will be referred to an alternate, general support group and informed about future offerings for which they might be eligible.

3.1 Inclusion Criteria

- 3.1.1 Documented cancer diagnosis within the WFBMC medical record;
- 3.1.2 Outpatient Cancer Survivor (diagnosis, treatment, or post-treatment);
- 3.1.3 Aged 18-39;
- 3.1.4 Must speak English
- 3.1.5 Must have computer with audio and visual capabilities.
- 3.1.6 Must live within North Carolina
- 3.1.7 Must have experienced health-related anxiety and/or distress in last 3 months.

3.2 Exclusion Criteria

Exclusion criteria will be determined by pre-screening data and medical chart reviews

- 3.2.1 Active inpatient hospitalization;
- 3.2.2 Major cognitive impairment, marked concerns with working memory, concentration, or word finding difficulties that significantly impairs daily functioning documented in most recent clinic note or self-reported;
- 3.2.3 Recent suicide attempt(s), psychiatric hospitalization, or psychotic processing (last 3 years);

Cancer within a Pandemic: A Telemental Health Intervention Designed to Augment Psychological Resilience amidst Dual Health Threats

Wake Forest Baptist Comprehensive Cancer Center
WFBCCC #01520

- 3.2.4 Bipolar disorder (I or II) diagnosis, as evidenced by an ICD-10 code within the past year or revealed during subject interview
- 3.2.5 Moderate to severe alcohol or drug abuse; as evidenced by an ICD-10 codes related to alcohol or illicit substance abuse in the medical record within the past year or revealed during subject interview.
- 3.2.6 Severe eating disorders; as evidenced by an ICD-10 code in the medical record such as anorexia nervosa or bulimia within the past year or revealed during patient interview
- 3.2.7 Repeated “acute” crises for example: repeated acute crises consisting of marked psychological distress that impairs function and warrants clinician intervention (e.g., occurring once a month or more frequently); this will be evaluated by the clinician screener

3.3 Inclusion of Women and Minorities

Men and women of all races and ethnicities who meet the above-described eligibility criteria are eligible to participate in this study.

Based on WFBCCC population estimates, we expect approximately 45% of participants to be women. Translating this to our sample size estimate of 15, we plan to enroll at least 7 women. Similarly, we expect approximately 3% of study participants to be Hispanic/Latino (N=~1). We plan to enroll at least 13% Black or African American (N=2). Due to the small sample size we do not anticipate recruiting American Indian/Alaska Native, or Asian subjects; however no eligible subjects will be denied participation. Should we not meet or exceed these estimates, the PI will engage the Office of Cancer Health Equity to discuss strategies to enhance recruitment in these target populations.

4 Registration Procedures

All patients entered on any WFBCCC trial, whether treatment, companion, or cancer control trial, **must** be linked to the study in EPIC within 24 hours of Informed Consent. Patients **must** be registered prior to the initiation of treatment.

You must perform the following steps in order to ensure prompt registration of your patient:

1. Complete the Eligibility Checklist (Appendix A)
2. Complete the Protocol Registration Form (Appendix B)
3. Alert the Cancer Center registrar by phone, *and then* send the signed Informed Consent Form, Eligibility Checklist and Protocol Registration Form to the registrar, either by fax or e-mail.

Contact Information:

Cancer within a Pandemic: A Telemental Health Intervention Designed to Augment Psychological Resilience amidst Dual Health Threats

Wake Forest Baptist Comprehensive Cancer Center
WFBCCC #01520

Protocol Registrar PHONE [REDACTED]

Protocol Registrar [contact]

Protocol Registrar E-MAIL ([contact])

*Protocol Registration is open from 8:30 AM - 4:00 PM, Monday-Friday.

4. Fax/e-mail ALL eligibility source documents with registration. Patients **will not** be registered without all required supporting documents.

Note: If labs were performed at an outside institution, provide a printout of the results. Ensure that the most recent lab values are sent.

To complete the registration process, the Registrar will:

- assign a patient study number
- other appropriate actions
- register the patient on the study

5.0 Study Outcomes and Study Measures

5.1 Primary Outcome

- 5.1.1 To measure self-efficacy for young adult cancer survivors navigating pandemic conditions.

5.2 Secondary Outcomes

- 5.1.2 To reduce depression and anxiety levels through meaning-making.

5.3 Exploratory Analyses

- 5.1.3 To assess the feasibility of conducting a telehealth support group for cancer survivors within a pandemic.
- 5.1.4 To assess YA cancer survivors' interest in participation in a telehealth support group within a pandemic.
- 5.1.5 To enhance participants' strategies for engaging social connectivity and reduce feelings of isolation amidst simultaneous forces promoting self-isolation (i.e., cancer diagnosis and pandemic).
- 5.1.6 To reduce feelings of helplessness.
- 5.1.7 To observe improvement in psychological resilience and flexibility skills in participants.
- 5.1.8 To increase distress tolerance.

Cancer within a Pandemic: A Telemental Health Intervention Designed to Augment Psychological Resilience amidst Dual Health Threats

Wake Forest Baptist Comprehensive Cancer Center
WFBCCC #01520

Table 1: Study Measures		
Type/Purpose of Measure	Variable	Measures
Primary Outcomes	Self-Efficacy	Cancer Behaviour Inventory-brief version (CBI-B)
Secondary Outcomes	Depression and Anxiety Level	CAS, MINI MAC, and Purpose in Life Test
Exploratory Analyses	Feasibility Interest Social Connectivity Psychological resilience and flexibility skills Helplessness and Hopelessness Distress tolerance	Number of subjects participating at the final visit Number of Sessions Attended UCLA Loneliness Scale Acceptance and Action questionnaire (AAQ) MINI MAC Impact of Event Scale (IES)

6.0 Intervention Plan

The study aims to initially recruit a single cohort of 15 patients. This is a virtual group interventional design in which investigators distribute the electronic assessment battery, perform the intervention, assess mid-way through, and reassess post-intervention. The virtual group will be conducted within a secure platform such as Microsoft WebEx. Assessments (pre-, post-, mid-way) will be distributed through REDCap, a secure virtual platform, as will session handouts and forms. If participants do not have headphones, these will be provided by the study team. The biostatistician will assist with the assessment of change over time within the instrumentation. The session content for this group is built on clinical experience and empirically informed practices, drawing upon elements of Acceptance and Commitment Therapy and Meaning Making approaches. Investigators/facilitators believe that in these unique times, it is optimal to pull elements from various (manualized) approaches that contribute important elements to the group experience. In short, we are making intentional decisions within session design in which we draw heavily from empirically supported practices yet combine them in a manner that seems appropriate for the circumstances based on clinical judgment.

The intervention will be conducted by graduate-prepared mental health providers who are licensed or working under the supervision of a licensed provider. Providers will co-facilitate at all times, with two providers available to respond to group dynamics and follow up with individual members as needed.

The clinicians leading the group will adhere to professional, legal, and ethical guidelines of confidentiality established by professional organizations and state law. Legal and ethical exceptions to confidentiality include: A clear or present danger that the patient intends to harm her/himself or another, knowledge of the abuse or neglect of a minor child or incapacitated adult, or responses to a court subpoena or as otherwise required by law. All members of the group will be required to sign confidentiality forms, in which they agree not to disclose

Cancer within a Pandemic: A Telemental Health Intervention Designed to Augment Psychological Resilience amidst Dual Health Threats

Wake Forest Baptist Comprehensive Cancer Center
WFBCCC #01520

to anyone outside the group any information that may help to identify another group member. This includes, but is not limited to names, physical descriptions, biological information, and specifics to the content of interactions with other group members.

6.1 Methods

Steps: (Conducted by the Psychosocial Oncology group)

1. Advertise and Identify Prospective Candidates
2. Screen all referred candidates on rolling basis
3. Send out pre-group assessments electronically for completion
4. Begin eight weeks of group work
5. Send out post-group assessments electronically for completion

Session Content

Adapted from Eilenberg, Frostholm, & Kronstrand 2014 with elements on meaning making from Breitbart & Poppito, 2005, rev. 2011:

Session 1: Introduction to ACT and Meaning Making

Summary: The purpose of the 1st session is to introduce the framework and form of the group, as well as expectations for the 8 sessions. Our main focus is on willingness to engage in treatment, a basic understanding of ACT, mindfulness, and the importance and sources of meaning making—creative, experiential, historical, and attitudinal. We will start to practice experiencing each from this first session. The purpose is to introduce the framework of the group, logistics, and to create a safe and accepting atmosphere. Furthermore, we will briefly introduce participants to an understanding of what health anxiety in the context of cancer is.

Session 2: Previous strategies for Anxiety Control

Summary: The purpose of this session is to examine the individual's control strategies and experiences in coping with health anxiety. We will introduce the concept of pain vs. suffering and how cancer can enhance life meaning, maintain life meaning, or create loss of meaning. The purpose is to help the individual to examine whether the previously used strategies have been effective in the short- and long-term in relation to living a values-based, meaningful life.

Session 3:Introduction to Values Based Living

Summary: The purpose of session 3 is to extend the insights and experiences from the last session in relation to the control agenda's limited effect on anxiety. Through experiential exercises, the effect of the control agenda is further tested and examined. Further, values-based living is introduced as an alternative to an avoidance and control-driven life. Values are introduced in the context of willingness and a discussion will introduce "Life as Legacy" both in the past, the here-and-now, and the future.

Session 4: Acceptance as an Alternative to Control

Cancer within a Pandemic: A Telemental Health Intervention Designed to Augment Psychological Resilience amidst Dual Health Threats

Wake Forest Baptist Comprehensive Cancer Center
WFBCCC #01520

Summary: The purpose of session 4 is to introduce acceptance as an alternative to attempting to control anxiety. The control-agenda is additionally challenged by looking at the lack of success in applying these strategies to internal states. Remind participants that mindfulness is a practice in willingness and that willingness may increase the ability to act on life. Acting on life includes being courageous, creative, and responsible.

Session 5: Defusion-A Method for Distancing Yourself from your Thoughts

Summary: The purpose of session 5 is to introduce the concept of defusion through various exercises. Participants experience the difference between being immersed in thoughts and experiencing distance from worrisome thoughts. Participants will be introduced to the techniques with a focus on creating distance from thoughts (e.g., Leaves on a Stream), as this can help the participant to act on thoughts and feelings in line with their values and purpose in life—rather than use control and avoidance behaviors. Experiential sources of love, beauty, and humor enhance one's ability to “Connect with Life.”

Session 6: Identifying and Clarifying Values

Summary: The purpose of session 6 is to help participants further identify and clarify their own values and meaning in life in order to provide direction in their lives when treatment ends. Value-based action is introduced as an opportunity to expand the participants' repertoire with activities other than avoidance behavior, control or excessive preoccupation with bodily sensations. Participants will engage in creating a legacy project to foster creative, experiential, historical, and attitudinal meaning making. .

Session 7: Practice Observing Yourself

Summary: The purpose of session 7 is to provide an understanding and personal experience of the observing self—the perspective from which you can create distance from your thoughts and work with mindfulness techniques. The concept of the observing self can be crucial in terms of creating willingness to experience difficult feelings and observe thoughts, etc. without having to react automatically.

Session 8: Living Your Values

Summary: The purpose of session 8 is to help the individual further clarify their values and purpose in life by defining specific value-based steps which can be taken moving forward. Participants will share their Legacy Projects. The group is prepared for the end of the program by working on how to manage obstacles while continuing to move forward in life. The group will process termination.

Social media:

Many virtual group members like to meet on their own exterior to group meetings. While we will not sponsor such activities, group members are free to create forums for such interaction. During our groundrules session, we will discuss potential pros and cons of engaging in such social interaction.

Cancer within a Pandemic: A Telemental Health Intervention Designed to Augment Psychological Resilience amidst Dual Health Threats

Wake Forest Baptist Comprehensive Cancer Center
WFBCCC #01520

6.1 Study-Related Activities

	Pre-Study ^a	Introduction to ACT and Meaning Making Week 1	Previous strategies for Anxiety Control Week 2	Introduction to Values Based Living Week 3	Acceptance as an Alternative to Control Week 4	Mid-Point Assessment	Defusion-A Method for Distancing Yourself from your Thoughts Week 5	Identifying and Clarifying Values Week 6	Practice Observing Yourself Week 7	Living Your Values Week 8	Post-study
Informed consent	X										
Demographics	X										
Medical history											
Pre-screening questionnaire:	X										
Group Evaluation Questionnaire:						X					X
Instrumentation Coronavirus Anxiety Scale (CAS)	X					X					X
Acceptance and Action Questionnaire (AAQ)	X					X					X
The Cancer Behaviour Inventory-brief version (CBI-B)	X					X					X
The Mini-Mental Adjustment to Cancer (MINI-MAC) 29-item questionnaire	X					X					X
UCLA Loneliness Scale Version 3	X					X					X
The Impact of Event Scale - Revised (IES-R)	X					X					X
The Purpose in Life Test	X					X					X
Group Sessions		X	X	X	X		X	X	X	X	

Cancer within a Pandemic: A Telemental Health Intervention Designed to Augment Psychological Resilience amidst Dual Health Threats

Wake Forest Baptist Comprehensive Cancer Center
WFBCCC #01520

^a The instruments are sent out the first week of ten weeks (week one=pre-intervention instruments sent; eight week intervention; post-instruments are pushed at week ten).

Cancer within a Pandemic: A Telemental Health Intervention Designed to Augment Psychological Resilience amidst Dual Health Threats

Wake Forest Baptist Comprehensive Cancer Center
WFBCCC #01520

6.2 Intervention Administration

Instrumentation

Coronavirus Anxiety Scale (CAS)

“CAS is a reliable instrument ($\alpha > .90$), with solid factorial (single-factor; invariant across sociodemographics) and construct (correlated with anxiety, depression, suicidal ideation, and drug/alcohol coping) validity. The diagnostic properties of the CAS (90% sensitivity and 85% specificity) are comparable to related screening instruments, such as the Generalized Anxiety Disorder-7” (Lee, 2020).

Acceptance and Action Questionnaire (AAQ)

Acceptance and Action questionnaire (AAQ) assesses psychological inflexibility. It has been found to have high internal consistency and reliability across different types of psychopathology illnesses and different target groups.

Cancer Acceptance and Action Questionnaire

This 18-item questionnaire is used to assess psychological flexibility in cancer patients. It presents experiences such as avoidance and painful memories.

The Cancer Behaviour Inventory-brief version (CBI-B)

12-item validated questionnaire used widely as a measure of self-efficacy for coping with cancer, derived from the longer 33-item version. CBI-B has been reported to have good internal reliability ($\alpha = 0.84$) and construct validity. The CBI-B measures coping self-efficacy.

The Mini-Mental Adjustment to Cancer (MINI-MAC) 29-item questionnaire

The Mini-MAC is a 29-item questionnaire measures patients’ present experiences using a 4-point Likert scale ranging from “Definitely does not apply to me” (1) to “Definitely apply to me” (4). Five subscales include: Helpless–Hopeless, Anxious Preoccupation, Cognitive Avoidance, Fighting Spirit and Fatalism.

UCLA Loneliness Scale Version 3

A 20-item scale designed to measure one’s subjective feelings of loneliness as well as feelings of social isolation. Participants rate each item on a scale from 1 (Never) to 4 (Often). The measure has high internal consistency (coefficient alpha = .96) and a test-retest correlation over a two-month period of .73.

The Impact of Event Scale - Revised (IES-R)

Cancer within a Pandemic: A Telemental Health Intervention Designed to Augment Psychological Resilience amidst Dual Health Threats

Wake Forest Baptist Comprehensive Cancer Center
WFBCCC #01520

A short, easily administered self-report questionnaire that has eight intrusion and eight avoidance items, derived from the original IES. Six additional items assess for hyperarousal.

The Purpose in Life Test

This self-report questionnaire has 20 items that measure a person's sense of purpose and meaning in life and is based on Viktor Frankl's Logotherapy (Davies et al., 2014). Good reliability has been found, with split-half reliability coefficients of .90.

Pre-screening questionnaire

This investigator-created instrument is designed to assess group suitability, with attention to inclusion and exclusion criteria. It also will include technology training for group technology requirements.

Group Evaluation Questionnaire

This investigator-created instrument is designed to assess satisfaction and solicit feedback. It also will have questions pertaining to engagement with other group members exterior to group meetings.

7.0 Adverse Event Reporting

7.1 Reporting of Unanticipated Problems, Adverse Events or Deviations

Due to the nature and scope of this study, we do not anticipate any adverse events. However, any unanticipated problems, serious and unexpected adverse events, deviations or protocol changes will be promptly reported by the principal investigator or designated member of the research team to the IRB and sponsor or appropriate government agency if appropriate. The PI will be responsible for the monitoring and reporting of any adverse events. The co-investigators will be consulted as appropriate. All problems having to do with subject safety will be reported by the PI to the IRB. Specifically, the following will be reported, in writing: 1) all serious adverse events associated with the study procedures, and/or 2) any incidents or problems involving the conduct of the study or participation, including problems with the recruitment and/or consent processes. The PI will provide a discussion of any problems noticed during each year in the course of the study to the IRB on an annual basis

7.2 WFUHS IRB AE Reporting Requirements

Any unanticipated problems involving risks to subjects or others and adverse events shall be promptly reported to the IRB, according to institutional policy. Reporting to the IRB is required regardless of the funding source, study sponsor, or whether the event involves an investigational or marketed drug, biologic or device. Reportable events are not limited to physical injury, but include psychological, economic and social harm. Reportable events may arise as a result of drugs, biological agents, devices, procedures or other interventions, or as a result of questionnaires, surveys, observations or other interactions with research subjects.

Cancer within a Pandemic: A Telemental Health Intervention Designed to Augment Psychological Resilience amidst Dual Health Threats

Wake Forest Baptist Comprehensive Cancer Center
WFBCCC #01520

All members of the research team are responsible for the appropriate reporting to the IRB and other applicable parties of unanticipated problems involving risk to subjects or others. The Principal Investigator, however, is ultimately responsible for ensuring the prompt reporting of unanticipated problems involving risk to subjects or others to the IRB. The Principal Investigator is also responsible for ensuring that all reported unanticipated risks to subjects and others which they receive are reviewed to determine whether the report represents a change in the risks and/or benefits to study participants, and whether any changes in the informed consent, protocol or other study-related documents are required.

Any unanticipated problems involving risks to subjects or others occurring at a site where the study has been approved by the WFUHS IRB (internal events) must be reported to the WFUHS IRB within 7 calendar days of the investigator or other members of the study team becoming aware of the event.

Any unanticipated problems involving risks to subjects or others occurring at another site conducting the same study that has been approved by the WFUHS IRB (external events) must be reported to the WFUHS IRB within 7 calendar days of the investigator or other members of the study team becoming aware of the event.

Any event, incident, experience, or outcome that alters the risk versus potential benefit of the research and as a result warrants a substantive change in the research protocol or informed consent process/document in order to insure the safety, rights or welfare of research subjects.

7.3 Data Safety and Monitoring

Since the study is a treatment for mental health concerns such as depression and anxiety, it is likely several participants may endorse clinical levels of each. Current/recent suicidality is an exclusion criteria for this study, therefore those who endorse that upfront will not be enrolled in the study and will be given alternative options (e.g., referred for other CPSP services). If a participant does express suicidal or homicidal ideation at any point throughout the 8 sessions, a therapist will engage them in a personal discussion outside of the group to further assess safety additionally, the study will require that patients allow us to have their preferred phone number and physical address on hand (we have in med chart but have them consent to us using for this purpose) so that appropriate follow-up after video sessions can occur if there is concern for personal harm or the need for a private conversation. Additionally the study team will request emergency contact information of a friend or family member who will be contacted in the event that the study team cannot reach the participant. If a patient endorses active suicidality during the group, we will refer them to appropriate follow up depending on the level (e.g., referred to CPSP individually, call 911/ED for imminent danger).

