Appendix A – Eligibility Checklist

IRB Protocol No.	WFBCCC Protocol No. 01520
Study Title: Cancer within a Pandemic: A Telehealth Intervention Designed to Augment Psychological Resilience amidst Dual Health Threats	
Principal Investigator: [name].	

Inclusion Criteria (as outlined in study protocol)	Criteria is met	Criteria is NOT met	Source Used to Confirm * (Please document dates and lab results)
Documented cancer diagnosis within the WFBMC medical record			
Meets all pre-screen eligibility criteria			
Outpatient Cancer Survivor (diagnosis, treatment, or post-treatment)			
Aged 18-39			
Must speak English			
Must have computer with audio and visual capabilities			
Must live within North Carolina			
Must have experienced health-related anxiety and/or distress in last 3 months			
Exclusion Criteria (as outlined in study protocol)	Criteria NOT present	Criteria is present	Source Used to Confirm * (Please document dates and lab results)
Active inpatient hospitalization;			
Major cognitive impairment, marked concerns with working memory, concentration, or word finding difficulties that significantly impairs daily functioning documented in most recent clinic note or self-reported;			
Recent suicide attempt(s), psychiatric hospitalization, or psychotic processing (last 3 years);			

Cancer within a Pandemic: A Telemental Health Intervention Designed to Augment Psychological Resilience amidst Dual Health Threats

Wake Forest Baptist Comprehensive Cancer Center
WFBCCC #01520

Bipolar disorder (I or II) diagnosis, as evidenced by an ICD-10 code within the past year or revealed during subject interview			
Moderate to severe alcohol or drug abuse; as evidenced by an ICD-10 codes related to alcohol or illicit substance abuse in the medical record within the past year or revealed during subject interview.			

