Severe eating disorders; as evidenced by an ICD-10 code in the medical record such as anorexia nervosa or bulimia within the past year or revealed during patient interview			
Repeated “acute” crises for example: repeated acute crises consisting of marked psychological distress that impairs function and warrants clinician intervention (e.g., occurring once a month or more frequently); this will be evaluated by the clinician screener			

This subject is eligible / ineligible for participation in this study.

OnCore Assigned PID: _____

Signature of research professional confirming eligibility: _____

Date: ____ / ____ / ____

Signature of Treating Physician: _____

Date: ____ / ____ / ____

Signature of Principal Investigator**: _____

Date: ____ / ____ / ____

* Examples of source documents include clinic note, pathology report, laboratory results, etc. When listing the source, specifically state which document in the medical record was used to assess eligibility. Also include the date on the document. Example: “Pathology report, 01/01/14” or “Clinic note, 01/01/14”

**Principal Investigator signature can be obtained following registration if needed

Cancer within a Pandemic: A Telemental Health Intervention Designed to Augment Psychological Resilience amidst Dual Health Threats

Wake Forest Baptist Comprehensive Cancer Center
WFBCCC #01520

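### Section 7.3 bars enrolment for current or recent suicidality, but neither the exclusion list in 3.2 nor the Appendix A checklist contains that criterion

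*Combined protocol and SAP*

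**What the plan says.** Section 7.3 (Data Safety and Monitoring) treats suicidality as a bar to entry: "Current/recent suicidality is an exclusion criteria for this study, therefore those who endorse that upfront will not be enrolled in the study". It adds that people turned away for this reason are offered other services.

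Section 3.2 gives seven numbered exclusions and says how they are applied: "Exclusion criteria will be determined by pre-screening data and medical chart reviews". The one item that mentions suicide, 3.2.3, reads "Recent suicide attempt(s), psychiatric hospitalization, or psychotic processing (last 3 years"). The nearest other item, 3.2.7, concerns "repeated acute crises consisting of marked psychological distress that impairs function and warrants clinician intervention", with a frequency of about monthly or more given as an example.

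Section 4 makes completion of the Appendix A checklist the first registration step. Appendix A reproduces the seven exclusions of 3.2 and adds none. Among its inclusion rows is one general entry: "Meets all pre-screen eligibility criteria".

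Section 6.2 describes the pre-screening questionnaire as an investigator-written form that assesses suitability for the group in light of the inclusion and exclusion criteria. Its items are not given.

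**The concern.** The safety section relies on an eligibility rule that is absent from the list and the form staff use to decide eligibility. Someone who works from 3.2 and Appendix A could, in good faith, register a person whom 7.3 says must not be enrolled.

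This matters more here than in many studies. Inclusion criterion 3.1.7 selects people with recent health-related anxiety or distress, 7.3 itself expects several participants to report clinical levels of depression or anxiety, and the intervention is a group delivered remotely. What is at stake is who enters the study and the safety of those people. No estimate or test is at stake.

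**Working it through.** No arithmetic applies beyond counting, so the check sets the texts side by side.

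**1. A test candidate against the list.** Take an outpatient aged 18 to 39 who meets all of 3.1 and has current suicidal ideation. This person has had no attempt, psychiatric admission or psychosis in the last 3 years, no repeated acute crises, and none of the other listed conditions.

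| Exclusion (3.2 and its Appendix A row) | Subject | Triggered by ideation alone? |
|---|---|---|
| 3.2.1 | Current inpatient stay | No |
| 3.2.2 | Major cognitive impairment | No |
| 3.2.3 | Suicide attempt, psychiatric admission or psychosis, 3 years | No |
| 3.2.4 | Bipolar disorder | No |
| 3.2.5 | Alcohol or drug abuse | No |
| 3.2.6 | Severe eating disorder | No |
| 3.2.7 | Repeated acute crises | No, because repetition is required |

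None of the 7 is triggered. Under 7.3 the same person is not to be enrolled.

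**2. The checklist as a whole.** Appendix A has 8 inclusion rows and 7 exclusion rows, 8 + 7 = 15. One row repeats 3.2.3, none names suicidality or ideation, and one (the general pre-screen row) could catch the candidate indirectly.

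**3. Whether the pre-screen closes the gap.** The general row works only if the pre-screen asks about ideation. Section 6.2 ties that form to the inclusion and exclusion criteria, and the list under that name in 3.2 omits this one. The contents page lists four appendices, A to D, and none is the pre-screening form, so its questions cannot be checked. It may already ask.

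**4. Other points at which the candidate might be stopped.** Appendix A has signature lines for the research professional, the treating physician and the principal investigator. All three sign the same rows, and a footnote says "Principal Investigator signature can be obtained following registration if needed", so that last signature is not a certain stop before registration. The baseline questionnaires go out after screening (6.1, steps 2 and 3). None of them is described in 6.2 as measuring suicidal ideation; the coronavirus anxiety scale is said only to correlate with it.

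**5. Look-back periods.** 3.2.3 gives 3 years. 3.2.4 to 3.2.6 give 1 year for diagnostic codes, for example "Bipolar disorder (I or II) diagnosis, as evidenced by an ICD-10 code within the past year or revealed during subject interview". Section 7.3 gives no period for what counts as recent.

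**6. What 7.3 means by suicidality.** Later in the same paragraph the term is used for something active that a participant endorses during the group, with follow-up graded by level. That fits a present state such as ideation better than a past attempt. It does not prove that the entry rule has the same meaning.

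**The case against.** The strongest reply is that the rule is already in the protocol. Section 7.3 states the exclusion, its consequence and the referral route, and it speaks of people who endorse suicidality before entry, which presupposes that the subject is raised. Section 6.2 does not confine the pre-screen to the numbered list, so a criterion that the protocol elsewhere calls an exclusion falls within its scope. A candidate stopped there would fail the general pre-screen row and be ineligible on the same form. Pre-screening is done by experienced psychosocial oncology investigators. On this view all that remains is incomplete cross-listing.

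Much of this is fair. The two texts do not contradict each other, since both can apply, and the pre-screen may well work as intended. But a rule that takes effect only if an unseen form happens to contain the question is weaker than one written into the list and the checklist.

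A second reply is that 7.3 is loose shorthand for 3.2.3, which also uses the word recent. This reading cannot be excluded. If it is right, 3.2 and Appendix A are complete and 7.3 promises more than the study does. The documents still need aligning; only the place of the correction changes.

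Third, the look-back point is modest. Current suicidality needs no window, and 3.2.2 and 3.2.7 also work without a fixed period. Only the word recent is left undefined.

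Finally, 7.3 has real safeguards for ideation that appears during the 8 sessions: private assessment by a therapist, contact details and an emergency contact on hand, and referral or emergency services according to level. These stand, but they act after enrolment, whereas the rule in question is meant to act before it.

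**Conclusion.** The concern holds. Section 7.3 is broader than the operative eligibility list, and on either reading one of them is wrong as written. The mismatch is complete for ideation without an attempt: 0 of 7 numbered exclusions and 0 of 15 checklist rows name it.

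That the wording differs is certain. Whether anyone would actually be enrolled against 7.3 depends on the pre-screening questions, which the documents do not show, and the number of candidates concerned, against a planned enrolment of 15, cannot be derived. The point should be fixed because it concerns participant safety at entry and is cheap to correct. It has no bearing on the endpoints, the sample size or the analysis.

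**What to change.** - Extend 3.2.3, or add a numbered exclusion, to cover current or recent suicidality including ideation. The clinical team should set the look-back and the threshold; because 3.1.7 already requires recent anxiety or distress, where to draw the line is a clinical choice.
- Add a matching row to the Appendix A exclusions.
- Confirm that the pre-screening questionnaire asks about it, or add one question.
- Use the same wording in 7.3.
- If only 3.2.3 was intended, reword 7.3 to match it and leave 3.2 and Appendix A as they are.

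No new referral text is needed, because 7.3 already provides for people who are turned away.

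The cost is a short wording amendment and at most one extra question in a telephone pre-screen that is already planned. A few candidates may be referred elsewhere, as 7.3 already intends. There are no added visits.
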